**SECONDARY OBJECTIVES**

- Evaluate the tolerability of the combination of blueberry extract and turmeric extract and study the plasma and tissue absorption of the active ingredients (anthocyanosides and curcumin);
- Evaluate the effects of treatment in the adjacent adenomatous and healthy tissue (perilesional) by evaluating the IHC expression of Nuclear Factor-K $\beta$  (NFK $\beta$ ), Ki-67, P53 apoptosis, tissue expression of the EGFRs system; tissue gene expression;
- Evaluate the modulation of some circulating growth factors in the collected serum: IGF system (IGF-I, IGFBP-3 and IGF-I/IGFBP-3), EGFR, inflammation markers (u-PCR).

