### **9.2 Secondary objectives**

1. Evaluate the effects of treatment on:

- oxidative stress and inflammation through the evaluation of IHC expression changes of Nuclear Factor-K $\beta$  (NFK $\beta$ ), one of the major transcription factors involved in the regulation of normal and neoplastic cells, closely related to the inflammatory and carcinogenic pathways of colon cancer;
- cell proliferation (Ki-67 labeling index), P53 mutation, tissue gene expression with microarray;
- circulating growth factors of the IGF system (IGF-I, IGFBP-3 and IGF-I/IGFBP-3) and EGFR;
- markers of inflammation (u-PCR).

2. Evaluate the tolerability of the treatment, as a combination of 2 food supplements and study the plasma and possibly tissue absorption of the active ingredients present in the botanical extracts (anthocyanosides and curcumin) .

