## **17.0 STATISTICAL METHODS**

### **17.1 Statistical design and sample calculation**

The primary endpoint of the study is the difference in  $\beta$ -catenin values [post-treatment value - pre-treatment value].

Data from our previous trial on the same study population (APAC Study) allow us to make some assumptions: we assume a baseline mean of  $\beta$ -catenin expression in adenomatous tissue equal to 25% (standard deviation=35) and a correlation between baseline and final  $\beta$ -catenin values equal to approximately 0.9. Given these assumptions, using an ANCOVA model (therefore adjusting the analysis for baseline  $\beta$ -catenin values), with 50 subjects per arm, for a total of 100 subjects, we will have an 85% power to observe a mean difference between the two arms equal to 10%, in the levels of  $\beta$ -catenin expression in adenomatous tissue. The sample calculation takes into account 10% of subjects lost to follow-up and a 2-tailed alpha error equal to 5%.

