### **17.3 Statistical analysis methods**

All subjects enrolled in the study will be considered in the “Intention To Treat” (ITT) population, and the statistical analysis will be performed in accordance with this principle, therefore considering the randomized subjects regardless of their actual adherence to the experimental treatment.

The descriptive statistics used for continuous variables will be: mean, standard deviation, median, quartiles, minimum and maximum; for discrete variables they will be: absolute frequency and relative frequency.

In agreement with previous results, the difference in post- and pre-treatment values of  $\beta$ -catenin [post-treatment value - pre-treatment value] is a normally distributed variable. However, the normality of the distribution will be tested and, if necessary, the necessary transformations will be applied to obtain normality.

Fisher's exact test and chi-square test will be used to compare proportions in the two treatment arms (toxicity: number of adverse events), while parametric (t-test) and non-parametric (Mann-Whitney U) tests will be used to compare continuous variables.

Parametric statistics will be used for the primary objective. Hypotheses will be tested using the general linear model: the null hypothesis of no treatment effect will be tested using standard analysis of variance (ANOVA) and covariance (ANCOVA) methods, adjusting for baseline  $\beta$ -catenin and the effect of other possible confounding factors such as age, sex, body mass index (BMI), family history of colon cancer, smoking habits, alcohol consumption and other important factors (demographic and/or biological) collected.

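### Microarray gene expression is a secondary objective, but section 17.3 gives it no analysis of its own and no control of false positives across genes

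*Combined protocol and SAP*

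**What the plan says.** Section 9.2 lists "cell proliferation (Ki-67 labeling index), P53 mutation, tissue gene expression with microarray" among the secondary objectives. The synopsis has the same objective without naming a platform, as "tissue expression of the EGFRs system; tissue gene expression", and places it among effects to be studied in both adenomatous and adjacent healthy tissue. Neither place calls it exploratory. Section 7.0 has tissue biomarkers measured in adenoma and normal tissue, before and after treatment.

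Section 17.3 holds the analysis methods. For continuous variables in general it says that "parametric (t-test) and non-parametric (Mann-Whitney U) tests will be used to compare continuous variables". The next paragraph opens with "Parametric statistics will be used for the primary objective" and goes on to ANOVA and ANCOVA in a general linear model, adjusted for baseline β-catenin and possible confounders.

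The only significance level in the plan is in section 17.1, where the sample-size calculation for the primary endpoint assumes "a 2-tailed alpha error equal to 5" per cent.

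No section gives, for the array, the number of genes, the filtering or normalisation, the model, a gene-level threshold, or a false discovery or familywise rule. No section has a multiplicity rule for the other secondary markers either.

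**The concern.** An array yields one comparison per gene, so a threshold that is tolerable for a single marker produces a long list of positives by chance alone. With nothing fixed in advance, the test, the filter and the threshold can all be chosen after the treatment codes are known. The study is titled as one of biomarker modulation, so its secondary biomarker results will be read closely. A list of modulated genes with no error control could not be told apart from noise.

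There is a second gap. The general t-test and Mann-Whitney line does not say whether post-treatment values or changes are compared, and it makes no use of a gene's own baseline value, although baseline tissue is collected. The ANCOVA text adjusts for baseline β-catenin, which is the wrong covariate for another gene or marker.

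**Working it through.** **1. The plan's own figure.** Inputs from 17.1: SD 35, baseline-final correlation 0.9, difference 10, 50 per arm less 10% loss = 45 per arm, two-sided 5%.
- ANCOVA: residual SD = 35 × √(1 − 0.9²) = 15.26; power 86.8% (noncentral t).
- Change score: SD = 35 × √(2 × (1 − 0.9)) = 15.65; power 85.0% (noncentral t).

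The stated 85% is reproduced. It concerns β-catenin only. The plan gives no figure for the array.

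**2. Expected false positives.** Suppose m genes are each tested at level α and none is affected. The expected number of positives is m × α. This holds whether or not the genes are correlated; correlation changes the spread of the count, not its mean. The value of m is an assumption throughout.

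| Assumed m | α = 0.05 | α = 0.01 |
|---|---|---|
| 1,000 | 50 | 10 |
| 5,000 | 250 | 50 |
| 10,000 | 500 | 100 |
| 20,000 | 1,000 | 200 |
| 50,000 | 2,500 | 500 |

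To reach 200 at α = 0.05 takes m = 200 / 0.05 = 4,000 genes. These counts are for one tissue; a second tissue gives a second list.

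**3. Simulation check.** Null genes, simulated as independent, 45 per arm, 20 runs for each m; mean number of positives per run:

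| Rule | m = 5,000 | m = 20,000 |
|---|---|---|
| t-test, p < 0.05 | 248 | 992 |
| Mann-Whitney, p < 0.05 | 247 | 981 |
| Either test, p < 0.05 | 295 | 1,184 |
| t-test with Benjamini-Hochberg at 5% | 0.05 | 0 |

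The first two rows agree with m × α. The third shows what is added if both tests are run and either may count. The last shows that false discovery control removes the problem when nothing is affected.

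**4. Use of baseline.** For baseline-final correlation r, the SD relative to a comparison of post-treatment values alone is √(1 − r²) for ANCOVA and √(2(1 − r)) for change scores.
- r = 0.9 (β-catenin, 17.1): 0.436 and 0.447.
- r = 0.7 (adenoma size, 17.2): 0.714 and 0.775.
- r below 0.5: the change-score ratio exceeds 1, while the ANCOVA ratio does not.

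With the β-catenin inputs of step 1, comparing post-treatment values alone would have power 26.8%, against 86.8% for ANCOVA. The documents give no r for genes, so this shows direction only.

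**The case against.** The strongest reply is that the plan is silent on the array rather than wrong. Section 17.3 mentions neither genes nor arrays, so gene-by-gene testing at 5% is an inference. The 5% level belongs to the primary sample-size calculation, and no passage says that a list of genes will be declared significant. This stands, and it makes the size of the problem conditional.

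It can also be said that ANCOVA is available. It is in 17.3, and 17.2 assumes it for adenoma size, which is not the primary endpoint. So the t-test and Mann-Whitney are not the only methods in the plan. But the ANCOVA text in 17.3 follows a sentence on the primary objective and names baseline β-catenin as the covariate. Read as widely as possible, it still supplies neither a gene's own baseline nor any error control.

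A reader might infer three stronger things, which the documents do not support:
- **That the trial would report hundreds of false gene effects.** This needs about 4,000 or more genes, mostly unaffected, tested at an unadjusted 5%. The plan states none of these.
- **That every variable would be tested twice.** The same sentence pairs Fisher's exact test with the chi-square test, which are customary alternatives. The two tests for continuous variables may be meant likewise, although no rule for choosing is given.
- **That the other secondary markers would more often than not yield a chance finding.** Counting 15 markers as independent gives 1 − 0.95^15 = 54%. The count is uncertain: P53 appears as a mutation in 9.2, so it may not be continuous, and the synopsis wording on P53 and apoptosis can be read as one item or two. The markers are also not independent, since one is the ratio of two others and the two tissues come from the same patients. With positive correlation the chance would be lower.

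**Conclusion.** The point holds in a conditional form. Microarray expression is a secondary objective with no array analysis and no error control, and the only tests clearly assigned to secondary continuous variables are unadjusted and ignore the variable's own baseline. If they were applied per gene at two-sided 5% with no true effect, about 5% of genes would be falsely positive: 50, 250 or 1,000 for an assumed 1,000, 5,000 or 20,000 genes. The proportion follows from the level; the counts rest on the assumed m.

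The primary β-catenin comparison and its power are untouched, and no decision rule in the plan depends on the secondary markers. This should be changed because it bears on how far the secondary biomarker results can be believed. It does not put the trial's main conclusion at risk.

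**What to change.** Add to 17.3:
- **Array data.** For each gene, a linear model of the post-treatment value on treatment, adjusted for that gene's baseline value, fitted separately for adenoma and healthy tissue. State normalisation and filtering before unblinding, with filtering blind to treatment arm.
- **Error control.** Benjamini-Hochberg within each tissue at one false discovery rate fixed before unblinding, for example 5%. Claim a treatment effect only for genes that pass, and make estimates for all genes available so that reporting is not selective.
- **Other secondary markers.** Baseline-adjusted estimates with 95% confidence intervals, labelled exploratory. Formal adjustment across this small panel is a trade-off and is not needed if no significance is claimed. A categorical P53 result needs its own stated comparison.

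False discovery control is preferable to Bonferroni here. At 0.05 / 20,000 = 2.5 × 10⁻⁶ and 45 per arm, an effect of the primary's standardised size (10 / 15.26 = 0.655) would be found with power of only about 5% (normal approximation).

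The cost is a few lines of text, with no new patients, samples or assays, and fewer nominally significant secondary results.

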### **11.3 Baseline Visit**

- Clinical visit and detection of vital parameters: weight, height, blood pressure (BP), Performance status (PS) according to ECOG;
- Blood sampling for the determination of circulating biomarkers and for the determination of plasma absorption of the active ingredients present in the botanical extracts at time zero (only for patients enrolled at the EO Ospedali Galliera).
- Delivery of the food diary.
- Anamnesis, concomitant pathologies and family history (I and II degree) for CRC/other neoplasms;
- Concomitant therapies;
- Randomization;
- Delivery of supplement/placebo: a package containing sufficient supplement for a six-week administration period + 6 spare tablets (90 tablets) will be delivered. The kit must be returned at the end of the study visit.

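### Section 17.3 does not fix one primary test: it names ANOVA beside the baseline-adjusted ANCOVA, leaves the covariates open, and omits the site strata

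*Combined protocol and SAP*

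**What the plan says.** Section 17.1 defines the outcome: "The primary endpoint of the study is the difference in" β-catenin values, post-treatment minus pre-treatment. It sizes the trial "using an ANCOVA model (therefore adjusting the analysis for baseline" β-catenin, and names no other covariate. It states that "with 50 subjects per arm, for a total of 100 subjects", "we will have an 85% power" to detect "a mean difference between the two arms equal to 10" percentage points. The inputs are SD 35, baseline-final correlation about 0.9, 10% lost to follow-up and two-sided alpha 5%.

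Section 17.3 puts the primary hypothesis in the general linear model and tests it by "standard analysis of variance (ANOVA) and covariance (ANCOVA) methods". It adjusts for baseline β-catenin and for other possible confounders. Age, sex and BMI are given as examples, and the list closes with "family history of colon cancer, smoking habits, alcohol consumption and other important factors (demographic and/or biological) collected".

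Section 10.5 stratifies the randomization by enrolling site. Neither 17.1 nor 17.3 mentions site as a model term.

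**The concern.** A confirmatory p-value keeps its 5% error rate only if the test behind it is fixed before the data are seen. Section 17.3 leaves three things undecided:

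- whether the primary null is tested by ANOVA, by ANCOVA or by both;
- which covariates enter the model, since the named factors are only examples and the word important has no definition;
- when those covariates must have been measured.

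The one factor that the design does call for, site, is missing. Each open choice yields another p-value for the same hypothesis. If the most favourable one were reported as primary, the true error rate would exceed 5%. Even if no one chose that way, a reader of the results could not verify it from the plan.

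**Working it through.** **Inputs (17.1).** Difference 10, SD 35, correlation r = 0.9, 50 per arm less 10% = 45 evaluable per arm, two-sided alpha 0.05.

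**1. Reproducing the stated 85% power.**

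- ANCOVA residual SD = 35 × √(1 − 0.9²) = 35 × √0.19 = 15.26. Standard error of the difference = 15.26 × √(2/45) = 3.216. Ratio = 10/3.216 = 3.11. Power = 86.8% (noncentral t, 87 df) or 87.5% (normal approximation).
- Change-score SD = 35 × √(2 × (1 − 0.9)) = 15.65. Power = 85.0% (t) or 85.8% (normal).

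The stated 85% is reproduced within two points by the t-based ANCOVA, and almost exactly by an unadjusted analysis of the change. The sample size is not in dispute.

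**2. The two sections side by side.**

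| Item | 17.1 | 17.3 |
|---|---|---|
| Method | ANCOVA | ANOVA and ANCOVA |
| Baseline β-catenin | yes | yes |
| Further covariates | none mentioned | six named as examples, plus an open clause |
| Selection rule | not needed | none |
| Timing limit on covariates | not needed | none |
| Enrolling site | absent | absent |

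No other section closes these choices.

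**3. What the open choice can do to type I error.** Data were simulated under no treatment effect, with 45 per arm and r = 0.9. Six covariates were assumed independent of each other and unrelated to outcome. A run counts as a false positive if any model in the set gives p < 0.05. Ranges are across separate simulations of 3,000 to 20,000 runs.

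| Models available | Type I error |
|---|---|
| One pre-set ANCOVA on baseline | 5.2% to 5.4% |
| One pre-set ANCOVA with six fixed covariates | 5.0% |
| Better of ANCOVA and change-score ANOVA | 6.1% to 6.6% |
| Better of baseline-only and six-covariate ANCOVA | 6.2% |
| Best of those three | 7.0% to 7.5% |
| Worst case: every subset of the six covariates | 8.7% to 9.2% |

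Monte Carlo standard error is √(0.05 × 0.95/10,000) = 0.2 points at 10,000 runs, and √(0.087 × 0.913/3,000) = 0.5 points at 3,000 runs. The single-model rows agree with 5% within that noise. The second row shows that adjustment itself is harmless when the list is fixed; the excess comes from choosing.

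**4. After the fix.** With arm and baseline only, power is 86.8%. The number of sites is not given. If site cost six further degrees of freedom (assumption) and explained nothing, power would be 86.7%, counting the loss of degrees of freedom alone.

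**The case against.** The strongest reply is that there is no real conflict. Section 17.1 is a sample-size paragraph, and its silence on further covariates contradicts nothing. ANOVA and ANCOVA can be read as naming the general linear model family. The sentence adjusts for baseline, which points to ANCOVA. This largely stands: the two sections share one core model, and the open covariate list is the stronger half of the point. It does not answer that list, which nothing closes.

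The reply also says, fairly, that the error rates assume the smallest p-value is picked after the results are seen. They are bounds on what the wording permits, not forecasts.

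A reader might infer more than the documents support:

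- **ANOVA on the final value alone.** This would have only 27% power, and adding it to the choice of ANCOVA or change score raises the error to 10.4%. But 17.1 defines the endpoint as the change, so this model should not be counted.
- **Adjustment for markers changed by treatment.** Biomarkers are also measured at end of treatment (7.0), and the wording does not exclude them. Yet 17.3 speaks of confounders, and no section proposes such adjustment. Any size for the harm would rest on an invented share of the effect.
- **Extra covariates add no power.** This holds only if they are irrelevant. If six covariates explained 10% of the residual variance, power would be 89.9%; at 20%, 93.0%. The documents give no share.
- **Power lost to missing covariates.** A fall to 80% to 82% needs all six to be missing independently in 2% to 3% of subjects, with complete-case analysis. Neither is stated. With two covariates so affected, power is 84.6% to 85.4%.
- **Smoking and alcohol not collected.** The baseline visit lists "Anamnesis, concomitant pathologies and family history (I and II degree) for CRC/other neoplasms", and history-taking may cover both. The case report form is not available to check.
- **An unblinded analyst choosing the model.** Sections 10.5 and 17.2 do not show that one biostatistician holds both roles, and the interim look covers adverse events and adenoma size, not β-catenin.

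**Conclusion.** The point holds as a pre-specification defect. The plan does not identify a single primary test, because 17.3 adds ANOVA, leaves the covariates and their timing open, and omits site. If the most favourable result were chosen, type I error would be about 6% to 7.5% over two or three plausible models, and about 9% in a worst-case search over six covariates, against a nominal 5%. These figures rest on 45 per arm, r = 0.9 (SD 35 only sets the scale), normal data, and covariates unrelated to outcome.

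It would be too strong to say that the two sections specify contradictory analyses, that the trial is underpowered, or that the effect estimate will be biased. The shared baseline-adjusted ANCOVA and the reproduced power argue against the first two, and nothing in the documents establishes the third. The correction is worth making because it costs almost nothing and removes the doubt.

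**What to change.** - In 17.1 and 17.3, name one primary model: ANCOVA on treatment arm, baseline β-catenin and enrolling site, with small sites pooled by a rule set before unblinding.
- If further covariates are wanted in that model, give a closed list of values recorded before randomization, fixed before unblinding.
- Delete ANOVA as a separate test of the primary null, and delete the closing clause that admits other important demographic or biological factors.
- Report all other adjusted models as sensitivity analyses.

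The cost is a few sentences, a few degrees of freedom for site, and less freedom in choosing covariates. The sample size of 100 is unchanged, with power of about 87%.
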